5.3.4 Supportive care guidelines for MK3475 (pembrolizumab)-related AEs

Pneumonitis: Steroids should be administered for grade ≥ 2 events (initial dose of 1-2 mg/kg/day prednisone or equivalent followed by a taper continued over no less than four weeks). MK3475 (pembrolizumab) should be withheld for grade 2 pneumonitis, and permanently discontinued for grade 3, grade 4, or recurrent grade 2 pneumonitis. Consider adding prophylactic antibiotics for opportunistic infections in the case of prolonged steroid administration.

Diarrhea/colitis: Subjects should be carefully monitored for signs and symptoms of enterocolitis such as diarrhea, abdominal pain, blood or mucus in stool, with or without fever. The potential risk of gastrointestinal perforation should be taken into consideration.

All subjects who experience diarrhea/colitis should be advised to drink liberal quantities of clear fluids. If sufficient oral fluid intake is not feasible, fluid and electrolytes should be substituted via IV infusion.

Steroids should be administered for grade ≥ 2 events (initial dose of 1-2 mg/kg/day prednisone or equivalent followed by a taper continued over no less than four weeks). MK3475 (pembrolizumab) should be withheld for grade 2 or 3 colitis, and permanently discontinued for grade 4 colitis.

T1DM (if new onset) or hyperglycemia: Insulin should be administered for T1DM and hyperglycemia, and MK3475 (pembrolizumab) should be withheld in cases of grade 3 or 4 hyperglycaemia until metabolic control is achieved. MK3475 (pembrolizumab) will be resumed when subjects are clinically and metabolically stable.

Hypophysitis: Steroids should be administered for grade ≥ 2 events (initial dose of 1-2 mg/kg/day prednisone or equivalent followed by a taper continued over no less than four weeks). Replacement of appropriate hormones should be administered as clinically indicated, and MK3475 (pembrolizumab) should be withheld for symptomatic hypophysitis until the event is controlled with hormone replacement.

Hepatotoxicity: Steroids should be administered [initial dose of 0.5-1 mg/kg/day (for grade 2 events) and 1-2 mg/kg/day (for grade 3 or 4 events) prednisone or equivalent followed by a taper continued over no less than four weeks]. MK3475 (pembrolizumab) should be withheld for grade

2 immune-related hepatitis, and permanently discontinued for grade 3 or 4 immune-related hepatitis.

Renal failure or nephritis: Steroids should be administered for grade ≥ 2 events (initial dose of 1-2 mg/kg/day prednisone or equivalent followed by a taper continued over no less than four weeks). MK3475 (pembrolizumab) should be withheld for grade 2 immune-related nephritis, and permanently discontinued for grade 3 or 4 immune-related nephritis.

Hyperthyroidism or hypothyroidism: Hypothyroidism may be managed with replacement therapy without treatment interruption and without steroids. Hyperthyroidism must be managed symptomatically and steroids should be administered for grade ≥ 2 events (initial dose of 1-2 mg/kg/day prednisone or equivalent followed by a taper continued over no less than four weeks). MK3475 (pembrolizumab) should be withheld for grade 2 hyperthyroidism, and permanently discontinued for grade 3 or 4 hyperthyroidism.

Management of infusion reactions: Signs and symptoms usually develop during or shortly after drug infusion and generally resolve completely within 24 hours of completion of infusion. Treatment guidelines for subjects who experience an infusion reaction associated with administration of MK3475 (pembrolizumab) are described in Table 5.

Table 5. Infusion reactions treatment guidelines

| NCI CTCAE v.4.0.3 grade | Treatment | Premedication at subsequent dosing |
|--|---|---|
| Grade 1 Mild reaction; infusion interruption not indicated; intervention not indicated | Increase monitoring of vital signs as medically indicated until the subject is deemed medically stable in the opinion of the Investigator | None |
| Grade 2 Requires infusion interruption but responds promptly to symptomatic treatment (e.g., antihistamines, NSAIDS, narcotics, and IV fluids); prophylactic medications indicated for ≤ 24 hours | 
Stop infusion and monitor symptoms. Additional appropriate medical therapy may include but is not limited to: Antihistamines, NSAIDS, acetaminophen, narcotics, and IV fluids.
 
Increase monitoring of vital signs as medically indicated until the subject is deemed medically stable in the opinion of the Investigator.
 | 
Subject may be premedicated 1.5 hours (± 30 minutes) prior to infusion of pembrolizumab with:
 
Diphenhydramine 50 mg orally (or equivalent dose of antihistamine)
 
Acetaminophen 500-1000 mg orally (or
 |

| NCI CTCAE v.4.0.3 grade | Treatment | Premedication at subsequent dosing |
|--|--|------------------------------------|
| | 
If symptoms resolve within one hour of stopping drug infusion, the infusion may be restarted at 50% of the original infusion rate (e.g., from 100 ml/hour to 50 ml/hour). Otherwise, dosing will be held until symptoms resolve and the subject should be premedicated for the next scheduled dose.
 
Subjects who develop grade 2 toxicity despite adequate premedication should be permanently discontinued from further trial treatment administration.
 | equivalent dose of antipyretic) |
| 
Grades 3- 4
 
Grade 3
 
Prolonged (e.g., not rapidly responsive to symptomatic medication and/or brief interruption of infusion); recurrence of symptoms following initial improvement; hospitalization indicated for other clinical sequelae (e.g., renal impairment, pulmonary infiltrates).
 
Grade 4
 
Life-threatening; pressor or ventilatory support indicated.
 | 
Stop infusion and monitor symptoms. Additional appropriate medical therapy may include but is not limited to: Antihistamines, NSAIDS, acetaminophen, narcotics, IV fluids, oxygen pressors, steroids, and epinephrine.
 
Increase monitoring of vital signs as medically indicated until the subject is deemed medically stable in the opinion of the Investigator.
 
Hospitalization may be indicated.
 
Subject is permanently discontinued from further trial treatment administration.
 | No subsequent dosing |
| Appropriate resuscitation equipment should be available in the room and a physician readily available during the period of drug administration. | | |

Common terminology criteria for adverse events: CTCAE; Intravenous: IV; National Cancer Institute: NCI; Non-steroidal anti-inflammatory agents: NSAIDS.

Other allowed dose interruption for pembrolizumab

Pembrolizumab may be interrupted for situations other than treatment-related AEs such as medical / surgical events or logistical reasons not related to study therapy. Participants should be placed back on study therapy within 3 weeks of the scheduled interruption, unless otherwise discussed with the Sponsor. The reason for interruption should be documented in the patient's study record.

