5.3.3 MK3475 (pembrolizumab)

AEs (both non-serious and serious) associated with MK3475 (pembrolizumab) exposure may represent an immunologic etiology. These AEs may occur shortly after study treatment initiation or several months after the last dose of treatment. MK3475 (pembrolizumab) must be withheld

for certain drug-related toxicities and severe or life-threatening AEs as per Table 4 below. Dose reduction of MK3475 (pembrolizumab) is not permitted.

MK3475 (pembrolizumab) should be permanently discontinued:

- For grade 4 toxicity except for endocrinopathies that are controlled with replacement hormones.
- If steroid dosing cannot be reduced to ≤ 10 mg prednisone or equivalent per day within 12 weeks.
- If a treatment-related toxicity does not resolve to grade 0-1 within 12 weeks after last dose of MK3475 (pembrolizumab).
- If any event occurs a second time at grade ≥ 3 severity (also for recurrent grade 2 pneumonitis).

Table 4. Dose Modification and Toxicity Management Guidelines for Immune-related AEs Associated with Pembrolizumab

| General instructions: | | | | |
|------------------------------|---|--------------------------------------|---|--|
| Immune-related AEs | Toxicity grade or condition (CTCAEv 4.0) | Action taken to pembrolizumab | irAE management with corticosteroid and/or other therapies | Monitor and follow-up |
| Pneumonitis | Grade 2 | Withhold | 
 • Administer corticosteroids (initial dose of 1-2 mg/kg prednisone or equivalent) followed by taper | 
 • Monitor participants for signs and symptoms of pneumonitis • Evaluate participants with suspected pneumonitis with radiographic imaging |
| | Grade 3 or 4, or | Permanently | | |

| | | | | |
|--|-------------------|---------------------------|---|--|
| | recurrent Grade 2 | discontinu e | | and initiate corticosteroid treatment 
 • Add prophylactic antibiotics for opportunistic infections |

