| Diarrhea / Colitis | Grade 2 or 3 | Withhold | 
 • Administer corticosteroids (initial dose of 1-2 mg/kg prednisone or equivalent) followed by taper | 
 • Monitor participants for signs and symptoms of enterocolitis (ie, diarrhea, abdominal pain, blood or mucus in stool with or without fever) and of bowel perforation (ie, peritoneal signs and ileus). • Participants with \geq Grade 2 diarrhea suspecting colitis should consider GI consultation and performing endoscopy to rule out colitis. • Participants with diarrhea/colitis should be advised to drink liberal quantities of clear fluids. If sufficient oral fluid intake is not feasible, fluid and electrolytes should be substituted via IV infusion. |
| | Grade 4 | Permanent ly discontinu e | | |
| AST / ALT elevation or Increased bilirubin | Grade 2 | Withhold | 
 • Administer corticosteroids (initial dose of 0.5-1 mg/kg prednisone or equivalent) followed by taper | 
 • Monitor with liver function tests (consider weekly or more frequently until liver enzyme value returned to baseline or is stable |
| | Grade 3 or 4 | Permanent ly discontinu e | 
 • Administer corticosteroids (initial dose of 1-2 mg/kg prednisone or equivalent) followed by taper | |

| | | | | |
|--|--|--|---|--|
| Type 1 diabetes mellitus (T1DM) or Hyperglycemia | Newly onset T1DM or Grade 3 or 4 hyperglycemia associated with evidence of β -cell failure | Withhold | 
 Initiate insulin replacement therapy for participants with T1DM Administer anti-hyperglycemic in participants with hyperglycemia | 
 Monitor participants for hyperglycemia or other signs and symptoms of diabetes. |
| Hypophysitis | Grade 2 | Withhold | 
 Administer corticosteroids and initiate hormonal replacements as clinically indicated. | 
 Monitor for signs and symptoms of hypophysitis (including hypopituitarism and adrenal insufficiency) |
| | Grade 3 or 4 | Withhold or permanently discontinue ¹ | | |
| Hyperthyroidism | Grade 2 | Continue | 
 Treat with non-selective beta-blockers (eg, propranolol) or thionamides as appropriate | 
 Monitor for signs and symptoms of thyroid disorders. |

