| | Grade 3 or 4 | Withhold or permanently discontinue ¹ | | |
| Hypothyroidism | Grade 2-4 | Continue | 
 Initiate thyroid replacement hormones (eg, levothyroxine or liothyroinine) per standard of care | 
 Monitor for signs and symptoms of thyroid disorders. |
| Nephritis and Renal | Grade 2 | Withhold | 
 Administer corticosteroids (prednisone 1-2 mg/kg or equivalent) followed by taper. | 
 Monitor changes of renal function |
| | Grade 3 or 4 | Permanent ly | | |

| | | | | |
|------------------------------|--|--|---|--|
| dysfunction | | discontinu e | | |
| Myocarditis | Grade 1 or 2 | Withhold | 
 Based on severity of AE administer corticosteroids | 
 Ensure adequate evaluation to confirm etiology and/or exclude other causes |
| | Grade 3 or 4 | Permanent ly discontinu e | | |
| All other immune-related AEs | Intolerable / persistent Grade 2 | Withhold | 
 Based on type and severity of AE administer corticosteroids | 
 Ensure adequate evaluation to confirm etiology and/or exclude other causes |
| | Grade 3 | Withhold or discontinu e based on the type of event. Events that require discontinu ation include and not limited to: Gullain- Barre Syndrome, encephaliti s | | |
| | Grade 4 or recurrent Grade 3 | Permanent ly discontinu e | | |

1. Withhold or permanently discontinue pembrolizumab is at the discretion of the investigator or treating physician.

NOTE:

For participants with Grade 3 or 4 immune-related endocrinopathy where withhold of pembrolizumab is required, pembrolizumab may be resumed when AE resolves to ≤ Grade 2 and is controlled with hormonal replacement therapy or achieved metabolic control (in case of T1DM).

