- Mild-easily tolerated: It does not interfere with normal daily activities. CTCAE grade 1.
- Moderate: It causes some interference with daily activities; may require intervention or treatment. CTCAE grade 2.
- Severe: Normal daily activities are substantially impaired; hospitalization and/or intervention or treatment is required. CTCAE grade 3 or 4.
- Fatal-death. CTCAE grade 5.
- Not applicable: Clinically significant and asymptomatic laboratory test abnormalities or abnormal assessments, for which no CTCAE grading guidance is applicable but which are considered as AEs.

A mild, moderate, or severe AE may or may not be serious (see definition below). These terms are used to describe the intensity of a specific AE. However, a severe AE (such as severe headache) may be of relatively minor medical significance and is not necessarily serious. For example, nausea lasting several hours may be rated as severe, but may not be clinically serious. Fever of 39°C that is not considered severe may become serious if it prolongs hospital discharge by a day. Seriousness rather than severity serves as a guide for defining regulatory reporting obligations.

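### For hypophysitis, Table 4 with its closing note and protocol section 5.3.4 give different conditions for restarting pembrolizumab after a grade 3-4 event, and different triggers for the hold

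*Protocol*

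**What the plan says.** Two adjoining protocol sections tell the site what to do with pembrolizumab in a patient with hypophysitis.

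**Section 5.3.3 and Table 4.** The text names Table 4 as the source for withholding. The hypophysitis row goes by grade: "Hypophysitis | Grade 2 | Withhold", and for grade 3 or 4 "Withhold or permanently discontinue". Footnote 1 adds: "Withhold or permanently discontinue pembrolizumab is at the discretion of the investigator or treating physician". For grade 3 or 4 immune-related endocrinopathies that are withheld, the closing note says that "pembrolizumab may be resumed when AE resolves to ≤ Grade 2 and is controlled with hormonal replacement therapy". The general list of reasons for permanent discontinuation in 5.3.3 includes this entry: "For grade 4 toxicity except for endocrinopathies that are controlled with replacement hormones". It also includes a second occurrence of any event at grade 3 or higher.

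**Section 5.3.4.** The steroid instruction uses grade: "Hypophysitis: Steroids should be administered for grade ≥ 2 events". The pembrolizumab instruction in the same paragraph does not. The drug "should be withheld for symptomatic hypophysitis until the event is controlled with hormone replacement". The paragraph gives no grade for the hold, no grade for restart and no discontinuation option.

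**The concern.** Section 5.3.4 reads as a restatement of Table 4. For pneumonitis, colitis, hepatitis and nephritis, its pembrolizumab action matches the table grade by grade, so a site has reason to rely on either place. For hypophysitis the two do not match.

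The restart condition matters most. Resuming a checkpoint inhibitor after a severe immune-related event is a safety decision, and the protocol gives two conditions for it, one stricter than the other.

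The mismatch also reaches the safety reporting. Protocol section 8.3 and SAP section 6.2.1 report action taken and study discontinuations. SAP section 5.1 has data management review dose adjustments that did not follow the protocol. Where the two passages differ, that review has no single standard.

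**Working it through.** The protocol states no figure on this point, so the check sets the passages side by side, case by case.

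| Case | Table 4, footnote 1 and note | Section 5.3.4 | Compatible? |
|---|---|---|---|
| Symptomatic, grade 2: hold | Withhold | Withhold | Yes |
| Symptomatic, grade 3-4: initial action | Withhold or stop for good, at the physician's discretion | Withhold | Yes, by withholding |
| After grade 3-4: hormone-controlled and now grade 2 or lower | May resume | Hold ends | Yes |
| After grade 3-4: hormone-controlled but still grade 3 | Condition for resuming not met | Hold ends | **No** |
| Grade 2 or higher without symptoms, if it occurs | Action by grade | No hold stated | **Differs** |
| Grade 1 with symptoms, if it occurs | No row, so no action stated | Withhold | **Differs** |

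**Restart.** The note joins two conditions, grade 2 or lower and hormonal control. Section 5.3.4 has only the second. The passages separate whenever the second is met and the first is not.

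The general list in 5.3.3 does not close this gap. Its grade 4 entry exempts hormone-controlled endocrinopathies from permanent discontinuation, so it does not remove a controlled event that is still grade 4. Its 12-week limit for a treatment-related toxicity to return to grade 0-1 bounds how long an event can remain open, but it does not say when dosing may restart within that time.

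**Trigger.** Table 4 uses grade and 5.3.4 uses symptoms. These coincide in the typical case. They part only in the last two rows. Those rows depend on how CTCAE grades hypophysitis, which the documents do not reproduce. The general intensity scale in section 7.1 describes the lowest level as "Mild-easily tolerated: It does not interfere with normal daily activities. CTCAE grade 1". That wording does not exclude symptoms, but it does not mention hypophysitis either.

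**Number of patients.** Section 1.10.4 puts clinically significant endocrinopathies at less than 5-10% of patients on these agents. With 44 planned patients:

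- 0.05 × 44 = 2.2
- 0.10 × 44 = 4.4

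These are upper limits for all endocrinopathies together, including thyroid and adrenal disease. The documents give no rate for hypophysitis alone and no split by grade, so the affected subset cannot be calculated.

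**The case against.** The strongest reply is that a site following Table 4 rarely breaches 5.3.4. Section 5.3.3 points to Table 4 for withholding in mandatory terms, whereas 5.3.4 is headed as supportive care guidance and is worded as advice. Silence in 5.3.4 about stopping for good does not forbid it, and the general list in 5.3.3 applies alongside it. Section 5.3 also allows dosing only when the clinical and laboratory findings are acceptable, so a hold is always available.

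Much of this stands, and it rules out several stronger readings that a reader might infer:

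- **That Table 4 and 5.3.4 contradict each other on stopping at grade 3-4.** They do not. Permanent discontinuation is a discretionary option beside withholding, and withholding satisfies both.
- **That sites are told to do opposite things.** For hypophysitis neither passage says to continue where the other says to hold. That pattern does exist for grade 2 hyperthyroidism, where Table 4 continues and 5.3.4 withholds, but not here.
- **That Table 4 directs dosing at grade 1.** It has no grade 1 row for hypophysitis. A missing row is not an instruction to dose, and a symptomatic grade 1 case is itself hypothetical.
- **That 2 to 4 patients each face conflicting instructions.** That range is a ceiling for all endocrinopathies, and symptomatic grade 2 hypophysitis is withheld under both passages.

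The reply does not resolve the restart condition. A reference to Table 4 for withholding is not a statement that it overrides a separate pembrolizumab instruction in the next section, and no text says that it does. The note is phrased as a permission, but a permission tied to two conditions is not met by one of them.

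**Conclusion.** The point holds in a limited form. For hypophysitis the protocol gives two restart conditions after a grade 3-4 event and two triggers for the hold. The restart difference is a real inconsistency with a safety bearing. The trigger difference is one of wording, and it bites only in marginal cases.

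The restart conclusion assumes that an event can be under hormonal control and still be graded 3 or higher. The note implies this by listing the two conditions separately. The trigger conclusion assumes that grade and symptoms can part, which the documents do not settle.

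Few patients can be affected, and their number cannot be derived. The CBR test, the sample size and the decision rule do not depend on this text. The correction is worth making because it is cheap and concerns restart after a severe immune-related event. It does not threaten the trial's conclusions.

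**What to change.** Reconcile the hypophysitis paragraph of section 5.3.4 with the general list in section 5.3.3, the Table 4 row, footnote 1 and the closing note, so that the protocol states one trigger for the hold and one restart condition. Alternatively, add a sentence saying which passage governs where they differ. If text is removed from one place, check that the reference in 5.3.3 to Table 4 still leads to an instruction for hypophysitis. The sponsor's clinical team must choose the rule, and this review takes no view on it.

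The cost is wording in the next amendment and a short clarification letter to sites. No analysis, sample size or data collection changes.

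### For hyperthyroidism of grade 2 or higher, protocol section 5.3.4 calls for a steroid course that the Table 4 management column does not list, so the two passages need to be reconciled into one instruction.

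*Protocol*

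**What the plan says.** Two operative parts of the current protocol cover treatment-emergent hyperthyroidism.

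- **Section 5.3.3, Table 4.** The relevant column is headed "irAE management with corticosteroid and/or other therapies". Its hyperthyroidism entry is "Treat with non-selective beta-blockers (eg, propranolol) or thionamides as appropriate", and no corticosteroid is named. On pembrolizumab, the grade 2 row reads "Hyperthyroidism | Grade 2 | Continue". At grade 3 or 4 the table offers withholding or permanent discontinuation, and its footnote 1 adds: "Withhold or permanently discontinue pembrolizumab is at the discretion of the investigator or treating physician".
- **Section 5.3.4, hyperthyroidism or hypothyroidism paragraph.** "Hyperthyroidism must be managed symptomatically and steroids should be administered for grade ≥ 2 events", with the regimen given as "initial dose of 1-2 mg/kg/day prednisone or equivalent followed by a taper continued over no less than four weeks". The paragraph then has pembrolizumab withheld at grade 2 and permanently stopped at grade 3 or 4.

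A lesser difference concerns high blood glucose. Section 5.3.4 says "Insulin should be administered for T1DM and hyperglycemia", while Table 4 reserves insulin for type 1 diabetes and otherwise says "Administer anti-hyperglycemic in participants with hyperglycemia".

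**The concern.** Both passages are instructions to sites, and they do not list the same drugs for the same event. The trial is multicenter, so two sites could each point to protocol text while one starts a steroid course and the other does not.

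Three things depend on which passage is followed:

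- **Patient safety.** The choice affects steroid toxicity and immunosuppression during immunotherapy, in a protocol whose section 5.5 otherwise restricts steroids.
- **Continued pembrolizumab.** Section 5.3.3 requires a permanent stop if steroids cannot be brought down to 10 mg/day of prednisone or less within 12 weeks. A patient who never starts steroids cannot meet that rule.
- **Reading of the safety tables.** SAP section 6.2.1 tabulates concomitant medication and the action taken for adverse events. Differences between patients in those tables could reflect which page a site consulted.

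**Working it through.** The plan gives no figure here to reproduce. The check is a comparison of the texts plus two short calculations of scale.

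**1. Side by side, hyperthyroidism**

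| | Table 4 (5.3.3) | Section 5.3.4 |
|---|---|---|
| Symptomatic treatment | Beta-blocker or thionamide | Required, agents not named |
| Steroids, grade 2 or higher | Not listed | Called for |
| Pembrolizumab, grade 2 | Continue | Withhold |
| Pembrolizumab, grade 3 or 4 | Withhold or stop, physician's choice | Stop permanently |

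**2. Does the omission in Table 4 carry meaning?** The table has ten event rows. Seven name corticosteroids in the management column: pneumonitis, diarrhea/colitis, liver tests, hypophysitis, nephritis, myocarditis and the row for all other immune-related events. Three do not: diabetes/hyperglycemia, hyperthyroidism and hypothyroidism. In section 5.3.4 the diabetes paragraph mentions no steroids, and hypothyroidism is expressly to be managed without them. Hyperthyroidism is therefore the only one of the three for which 5.3.4 calls for steroids. For pneumonitis, colitis, liver toxicity and nephritis the two places give the same starting range. The hyperthyroidism row breaks that pattern.

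**3. Does the broken table layout matter?** In the text as read, the drug entry sits beside grade 2 and the grade 3 or 4 cell is empty, probably because the cells were merged. On either reading, no steroid is listed at any grade.

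**4. Size of the steroid dose.** The documents give no body weight, so I assume 50 to 90 kg.

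- Lowest initial dose: 1 mg/kg × 50 kg = 50 mg/day.
- Highest initial dose: 2 mg/kg × 90 kg = 180 mg/day.
- Relative to the 10 mg/day that section 5.5 treats as the physiologic ceiling: 50/10 = 5 and 180/10 = 18, so 5 to 18 times.

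This is the starting dose only. The four weeks is the minimum length of the taper that follows.

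**5. Upper limit on patients.** Section 1.10.4 gives less than 5-10% for all clinically significant endocrinopathies with anti-PD-1 and anti-PD-L1 agents. With 44 patients, 44 × 0.05 = 2.2 and 44 × 0.10 = 4.4. That section names hypophysitis and autoimmune thyroid disease, mainly hypothyroidism, as the most common, and mentions hyperthyroidism only as also reported. Grade 2 or higher hyperthyroidism is therefore some unstated part of a figure that is itself below about 2 to 4 patients.

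**The case against.** The strongest reply is that the two passages can both be obeyed. Table 4 does not prohibit steroids, and section 5.3.4 joins symptomatic treatment and steroids in one sentence, so a beta-blocker or thionamide plus a steroid satisfies both. Where the protocol wants no steroids it says so, as for hypothyroidism, and section 5.5 permits them for suspected immunologic events. This stands as far as it goes: it rules out reading Table 4 as an order to give none. It does not remove the problem, because a site using the table has no cue that a steroid course is expected. It also does nothing for the pembrolizumab action, where continuing and withholding at grade 2 cannot both be done.

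A second reply is that the General instructions row of Table 4 is empty in the available text and might have addressed precedence. That cannot be excluded, and the blank should not be counted as a gap in the plan.

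A third is that the steroid stopping rule adds little. Under section 5.3.4, grade 3 or 4 already means a permanent stop, so within that section the rule could add a discontinuation only at grade 2. This also stands.

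A reader might infer that the same patient will receive a month of high-dose steroid at one site and none at another. The documents support only that treatment could differ: section 5.3.4 says steroids should be given, Table 4 is silent, and no text prescribes four weeks at the initial dose. A reader might also treat the hyperglycemia wording as an equal conflict. It is not, because insulin is itself an anti-hyperglycemic and giving it meets both texts; one is simply narrower.

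**Conclusion.** The inconsistency is real and should be corrected. Section 5.3.4 calls for steroids in hyperthyroidism of grade 2 or higher; Table 4, in the column where it names steroids for other events, lists none. Where it applies, the difference in treatment is large: on the assumed weights, an initial 50 to 180 mg/day against nothing listed.

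Few patients are likely to be concerned. Their number cannot be derived from the documents and lies below the endocrinopathy bound, provided that grade 2 or higher hyperthyroidism falls within what section 1.10.4 calls clinically significant and that its rates carry over to this combination. It would be wrong to quote 2 to 4 patients as the affected group.

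A reader might also infer a threat to the primary analysis. Nothing here shows a material effect on the clinical benefit rate or on any other efficacy analysis. This is an internal inconsistency in safety instructions. The finding assumes that no precedence statement exists in text that could not be read.

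**What to change.** Reconcile the hyperthyroidism row of Table 4 with the hyperthyroidism paragraph of section 5.3.4 so that one instruction on steroids remains. In the same edit, reconcile the pembrolizumab action at grade 2 and at grade 3 or 4. State that the table and section 5.3.4 are to read the same. The medical monitor should decide which text is kept; this review takes no position on that. The hyperglycemia wording may be aligned at the same time for tidiness.

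The cost is a change of wording in sections 5.3.3 and 5.3.4, made through the amendment route in section 12.2. It adds no visits, data or analyses and does not affect the sample size.

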1.10.4 Endocrinopathies

Inflammation of the pituitary, thyroid, or adrenal glands as a result of checkpoint blockade often presents with imprecise symptoms such as nausea, headache, fatigue, and vision changes. Although it has been difficult to establish the exact incidence of endocrinopathies associated with these compounds, clinically significant events are thought to occur in less than 5-10% of patients treated with anti-PD-1 and anti-PD-L1 agents. The most common endocrinopathies are hypophysitis and autoimmune thyroid disease, principally primary hypothyroidism secondary to a destructive thyroiditis. Hyperthyroidism associated with Graves disease and adrenal insufficiency have also been reported with these compounds.

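### Hyperthyroidism: at grade 2, Table 4 keeps pembrolizumab going and Section 5.3.4 withholds it; at grade 3-4, Table 4 gives discretion where 5.3.4 calls for a permanent stop

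*Protocol*

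**What the plan says.** Three places in the protocol bear on pembrolizumab when hyperthyroidism occurs.

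- **Section 5.3.3, Table 4.** The grade 2 row reads "Hyperthyroidism | Grade 2 | Continue". The treatment column says: "Treat with non-selective beta-blockers (eg, propranolol) or thionamides as appropriate". For grade 3 or 4 the table allows either withholding or a permanent stop, and footnote 1 adds: "Withhold or permanently discontinue pembrolizumab is at the discretion of the investigator or treating physician". A note below the table lets pembrolizumab be resumed after a grade 3 or 4 endocrinopathy that has improved to grade 2 or lower and is controlled.
- **Section 5.3.3, text before Table 4.** Pembrolizumab must be withheld "for certain drug-related toxicities and severe or life-threatening AEs as per Table 4 below". A separate list of reasons for permanent discontinuation includes "For grade 4 toxicity except for endocrinopathies that are controlled with replacement hormones".
- **Section 5.3.4.** Pembrolizumab "should be withheld for grade 2 hyperthyroidism, and permanently discontinued for grade 3 or 4 hyperthyroidism". On treatment: "Hyperthyroidism must be managed symptomatically and steroids should be administered for grade" 2 and above, starting at prednisone 1-2 mg/kg/day or equivalent, with a taper of at least four weeks.

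**The concern.** Sections 5.3.3 and 5.3.4 are adjacent, both are current text, and both instruct the investigator on the same drug for the same event. At grade 2 the instructions are opposite. Depending on the page consulted, the same patient stays on pembrolizumab with a beta-blocker or thionamide, or is taken off it and started on high-dose steroids. At grade 3, one patient could later resume a study drug that another loses permanently.

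The stake is patient safety and uniform conduct across sites. There is also a practical problem for deviation review. SAP Section 5.1 lists dose adjustments not made as the protocol directs, and at grade 2 either action departs from one of the two texts.

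**Working it through.** The plan states no figure on this point, so the main check is a comparison by grade.

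| Item | Table 4 (5.3.3) | Section 5.3.4 | Can both be followed? |
|---|---|---|---|
| Pembrolizumab, grade 2 | Continue | Withhold | No |
| Pembrolizumab, grade 3-4 | Withhold or stop, physician's choice; resumption possible under the note | Stop permanently | Only by stopping permanently |
| Steroids, grade 2 and above | None named; beta-blockers or thionamides | Prednisone 1-2 mg/kg/day, taper of at least four weeks | Yes, but the requirement appears in one place only |

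**Grade 4 has a third rule.** The stop list in 5.3.3 requires permanent discontinuation at grade 4 unless the event is an endocrinopathy controlled with replacement hormones. Table 4 does not treat hyperthyroidism with replacement hormones, so it is unclear whether the exception applies. If it does not, the stop list removes the discretion that Table 4 gives at grade 4.

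**Comparison with other events.** For pneumonitis, colitis, hepatitis, nephritis and hypothyroidism, the pembrolizumab actions in 5.3.4 agree with Table 4. Hyperthyroidism breaks that pattern without explanation, which suggests a drafting error.

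**How many patients.** Section 1.10.4 gives no hyperthyroidism rate; it says only: "Hyperthyroidism associated with Graves disease and adrenal insufficiency have also been reported with these compounds". It puts all clinically significant endocrinopathies at less than 5-10%. With 44 patients, the ceiling for all of them together is:

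- 0.05 × 44 = 2.2
- 0.10 × 44 = 4.4

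Hyperthyroidism is only part of that. For an assumed hyperthyroidism rate p, the expected number is 44p and the chance of at least one case is 1 − (1 − p)^44:

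| Assumed p | Expected cases | Chance of at least one |
|---|---|---|
| 1% | 0.44 | 1 − 0.99^44 = 0.357 |
| 3% | 1.32 | 1 − 0.97^44 = 0.738 |
| 5% | 2.20 | 1 − 0.95^44 = 0.895 |

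Appendix 1 schedules TSH, free T3 and free T4 every two cycles, so thyroid changes will be looked for.

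**Size of the steroid difference.** For an assumed body weight of 50-90 kg, the 5.3.4 starting dose runs from 1 × 50 = 50 mg to 2 × 90 = 180 mg prednisone a day. Table 4 names none.

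**The case against.** The strongest reply is that Table 4 governs. The mandatory sentence in 5.3.3 points to Table 4 for withholding, while 5.3.4 is headed as supportive care guidance and says what should be done. That favours Table 4 and makes it the natural text to keep. It does not settle the matter: no readable text says that Table 4 overrides 5.3.4, Table 4 is itself titled as guidelines, and the permanent-stop list in 5.3.3 also uses the word should. The general-instructions row of Table 4 is empty in the text available for review, so a rule of precedence there cannot be excluded. The sponsor can check this against the original.

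It is also fair to say that grade 3-4 is the weaker half. Section 5.3.4 is a narrower instruction nested in a wider one, and a physician who stops permanently satisfies both. One who only withholds departs from 5.3.4, and the note on resumption widens that gap.

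On size, the assumed rates have no source in the documents. A 5% hyperthyroidism rate would use up the whole of the lower ceiling for all endocrinopathies, so the 90% figure is the top of the range and not a forecast. Section 5.3 lets eribulin continue when a toxicity is attributed solely to pembrolizumab, so a hold need not stop all treatment. Nothing shows that either action at grade 2 would be classed as a major deviation, so no consequence for the per-protocol set follows.

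**Conclusion.** The concern holds. The grade 2 instructions are incompatible in current text. The grade 3-4 instructions differ in whether the physician has a choice, and the grade 4 position is further unsettled by the stop list in 5.3.3. Confidence is high that the texts differ. That nothing resolves the difference is subject to the unreadable row of Table 4.

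Probably only a few of the 44 patients are affected: about 0.4 to 2.2 expected under assumed rates of 1% to 5%. For each one, the two texts lead to materially different care. No effect on the clinical benefit rate, PFS censoring or the per-protocol analysis is shown or claimed. It should be fixed because it concerns when to hold a study drug and the correction is small.

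**What to change.** By protocol amendment and site notice, leave one pembrolizumab instruction per grade.

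1. If the sponsor's medical team confirms Table 4, delete the hyperthyroidism wording on steroids, withholding and discontinuation from 5.3.4 and replace it with: *For hyperthyroidism, pembrolizumab action and treatment follow Table 4.* If the team prefers the 5.3.4 rule, change the Table 4 cells instead.
2. In the same amendment, state whether the grade 4 stop rule in 5.3.3 applies to hyperthyroidism. Editing 5.3.4 alone leaves grade 4 open.
3. If Table 4 is kept, its note on resumption is kept too. Its conditions are hormone replacement or, for type 1 diabetes, metabolic control, so a phrase saying what counts as control for hyperthyroidism would help.

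The cost is two or three sentences and a site notice. Design, sample size and analysis do not change.
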